4.2 INTERIM EFFICACY ANALYSIS

A single interim efficacy analysis will be conducted when 75% of the subjects (ie, ~100 subjects) have completed the 26-week Treatment Period if both of the following criteria are met: a) the expected time to randomize the final (136th) subject is greater than 3 months; b) at least 90% of the 6MWD data is present for both Period 1: Baseline and Week 12 and Period 2: Baseline and Week 12 for these subjects. The projected time to randomize will be based on the average recruitment rate for the prior 6 months. This plan will allow early stopping for efficacy if recruitment is slow enough to warrant an interim review and if the data are sufficiently complete.

A non-binding futility analysis will also be conducted as part of the interim analysis. Analyses will be conducted for the primary endpoint of 6MWD per Section 9.1. Analyses will use the entire Full Analysis Population (FAS), including all available data for subjects who may be still ongoing in the study. The independent external statistical consultant will provide the results of these analyses to the independent Data Safety Monitoring Committee (DSMC) for their review and recommendation. The Sponsor will remain fully blinded throughout this process.

The DSMC Charter will contain more specific details regarding the processes for the interim analyses for efficacy and futility, such as timelines for data lock, information transfer and communications. However, the following approaches will be taken for projecting recruitment and the criteria for the interim analyses for efficacy.

4.2.1

[REDACTED]

[REDACTED]

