4.2.2 Formal Criteria for Interim Efficacy Analyses

If conducted, the interim analysis will apply a 2-sided alpha level of 0.010 (75% information fraction), and at the final analysis at a 2-sided alpha of 0.022 with the overall Type I error rate at 2-sided alpha of 0.05. Efficacy boundaries for early stopping of the study for efficacy are based

¹ Subjects who were active in the treatment periods of this protocol as of 13 March 2020 will be assessed on a case-by-case basis by the Sponsor for inclusion of populations for adaptive, interim, and final analyses. All decisions will be documented and presented in the clinical study report.

on a Lan-DeMets spending function, with an O'Brien-Fleming boundary (GD-INFO; EAST[®], Cytel, Version 6.5). The corresponding non-binding futility boundary is provided as p-value less than or equal to 0.227 for the interim analysis (Lan-DeMets: O'Brien-Fleming).

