7.5 EXAMINATION OF SUBGROUPS

Primary and secondary efficacy analyses will be conducted on the FAS. Subgroup analyses will be performed to explore the efficacy of treprostinil in different subject populations. The subgroups will include, but not be limited to:

- age (<65, ≥65 years);
- sex (males, females);
- race (White, Black or African-American, Asian, American Indian or Alaskan Native, Native Hawaiian or Other Pacific Islander);
- ethnicity (Hispanic or Latino, non-Hispanic or Latino);
- age at WHO Group 3 PH-COPD diagnosis (date of diagnosis minus date of birth, in years, by quartiles);
- pulmonary vascular resistance (PVR; during screening, in quartiles);
- mean pulmonary artery pressure (mPAP; during screening, in quartiles);
- baseline (Day 1) 6MWD (≤350 meters versus >350 meters);
- baseline (Day 1) Borg dyspnea score (in quartiles).

Unless otherwise prespecified, continuous covariates will be presented by quartiles.

Comparative results will be presented using point estimates and associated 95% CIs both in tables and forest plots. Because the study was not designed to have high power for small or even moderate sized subgroups, these analyses will be considered exploratory. No Type 1 error adjustments will be performed for these subgroup analyses.

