9 EFFICACY ANALYSES

The following describes the planned primary endpoint analysis using 6MWD if the alternative primary endpoint analysis is not enacted. For details about the alternate primary endpoint and analysis, see Section 9.2. All efficacy analyses will be performed on the FAS (see Section 8). Additional supportive analyses will be conducted on the PPROT, as outlined below.

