9.1.2 Primary Efficacy Analysis Data

The primary efficacy analysis will be based on all available measurements of the 6MWD for the FAS as observed in the study, with the exception that for subjects whose 6MWD measures at Week 6 or Week 12 of either Period are missing due to death or being too ill to perform 6MWT, the missing values will be imputed as the worst possible score (0 meter) and change-from-baseline scores calculated. For missing data due to any other reason, the missing value will not be imputed.

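### SAP footnote 1 lets the sponsor decide case by case which subjects active on 13 March 2020 enter the adaptive, interim and final populations, with no visible criterion and no visible deadline before the adaptive or interim counts

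*SAP*

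**What the plan says.** The footnote is printed within SAP 4.2.2; the place in the text that it hangs from is not visible. It covers a cohort fixed by date, those "active in the treatment periods of this protocol as of 13 March 2020 will be assessed on a case-by-case basis by the Sponsor". The scope of that assessment is given as "for inclusion of populations for adaptive, interim, and final analyses". Its one stated control is reporting: "All decisions will be documented and presented in the clinical study report".

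Other visible SAP text describes the populations and data without such an exception:

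- SAP 4.2, on the interim: "Analyses will use the entire Full Analysis Population (FAS), including all available data for subjects who may be still ongoing in the study".
- SAP 7.5: "Primary and secondary efficacy analyses will be conducted on the FAS".
- SAP 9.1.2: "The primary efficacy analysis will be based on all available measurements of the 6MWD for the FAS as observed in the study".
- SAP 7.6 lists truncation by COVID-19 among the reasons for an incomplete treatment period. It then says that available data from every patient will be used in the way the plan details.

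Protocol 10.3 defines the Full Analysis Population as every randomized subject with at least one dose, and makes it the default for efficacy. The surviving end of the SAP's analysis-population section, printed after 5.2, requires exclusions from any population to be listed with reasons. The sponsor must approve that list before unblinding and so before the final analyses.

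**The concern.** Two decisions depend on how complete the data are. SAP 4.1 keeps the crossover if Week 25 presence is at least 85% for 6MWD or actigraphy, and otherwise switches to the parallel design. SAP 9.2.1 keeps 6MWD as primary endpoint if at least 65% of the key-visit values are present; below that, the endpoint may switch to the combined 6MWD/MVPA ranks. The first check is meant to measure dropout and lack of measurement. The second (SAP 4.3) is meant to measure 6MWD lost to COVID-19.

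The footnote gives subject-by-subject discretion over who is counted, for the cohort that was in treatment when the pandemic disrupted visits. Protocol 10.2 presents the design switch as automatic. A denominator settled by individual judgement, with no visible rule or date, does not fit that description. The same discretion reaches the final population, where leaving out subjects with incomplete data could move the estimate toward those who completed.

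**Working it through.** **Inputs.** From the documents: the 85% rule (SAP 4.1), the 65% rule with four key visits, Weeks 1, 12, 14 and 25 (SAP 9.2.1), 136 planned subjects and a 30 m effect (SAP 5.1), and an interim at about 100 subjects (SAP 4.2). Assumed, because the documents do not give them: the number excluded (k), the number due at Week 25 when the first check is made (N), and the values present per excluded subject (v).

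**The plan's own figures.** 75% of 136 is 102, stated as about 100. SAP 9.2.1 ties its threshold to about 88 evaluable subjects: 88/136 = 64.7%, rounded to 65%. Both reproduce. The footnote has no figure of its own.

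**85% rule.** If the k excluded subjects all lack Week 25 data, presence goes from P/N to P/(N − k). The lowest P that reaches the threshold is 0.85 × (N − k), rounded up.

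- N = 60, k = 2: 50/60 = 83.3% becomes 50/58 = 86.2%.
- N = 60, k = 5: 47/60 = 78.3% becomes 47/55 = 85.5%.
- N = 60, k = 10: 43/60 = 71.7% becomes 43/50 = 86.0%.
- N = 80, k = 5: 64/80 = 80.0% becomes 64/75 = 85.3%.
- N = 80, k = 10: 60/80 = 75.0% becomes 60/70 = 85.7%.
- If all 102 randomized were due, k = 1: 86/102 = 84.3% becomes 86/101 = 85.1%.
- Opposite direction, leaving out three subjects who have data: 87/102 = 85.3% becomes 84/99 = 84.8%.

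**65% rule.** 136 × 4 = 544 values. Presence goes from P/544 to (P − kv)/(544 − 4k).

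- v = 1 (baseline only), k = 5: 346/544 = 63.6% becomes 341/524 = 65.1%.
- v = 1, k = 10: 338/544 = 62.1% becomes 328/504 = 65.1%.
- v = 2, k = 10: 348/544 = 64.0% becomes 328/504 = 65.1%.
- v = 3 (cut short in Period 2), k = 10: 354/544 = 65.1% becomes 324/504 = 64.3%, so the decision can move the other way.

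More exclusions widen these ranges. At k = 20, the lowest presence that can be lifted to 85% is 34/60 = 56.7% or 51/80 = 63.8%. For the 65% rule it is 322/544 = 59.2% (v = 1) or 342/544 = 62.9% (v = 2).

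**90% interim gate.** The effect here is limited. The gate concerns subjects who completed treatment and asks for data "for both Period 1: Baseline and Week 12 and Period 2: Baseline and Week 12 for these subjects". Excluding completers also delays the trigger of about 100 subjects.

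**Estimate.** Suppose excluded subjects have zero effect, the rest have 30 m, and all carry equal weight. The estimate with everyone is 30 × (N − k)/N, and exclusion raises it to 30, a shift of 30k/N. With N = 136 this is 1.1 m (k = 5), 2.2 m (k = 10) or 4.4 m (k = 20). With N = 100 and k = 10 it is 3.0 m. This is an illustration, not a bound. Incomplete subjects carry less weight in the mixed model, which makes the shift smaller. Deaths and subjects too ill to walk are imputed at 0 m (SAP 9.1.2), so excluding such subjects could make it larger.

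**The case against.** The strongest reply is that much of the relevant text cannot be seen. The SAP's own FAS definition (Section 6), all of 4.2.1 and parts of the preface are redacted or missing, and SAP 4.2 sends the interim's data-lock timelines to the DSMC Charter. Any of these may hold a criterion or a date. A reader might infer that the footnote contradicts the SAP's definition of the FAS. The documents do not support that: the visible passages say which population is used, not who belongs to it, and the data-use sentence in 7.6 is qualified by reference to the plan itself. This part of the objection stands. The conflict is limited to the visible rules and the protocol's definition.

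A reader might also call the footnote a protocol violation. It is not one in itself, because Protocol 10 lets the SAP change methods before database lock, and 10.3 lets another population be specified. But a case-by-case choice does not specify a rule.

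The footnote speaks of assessment for inclusion and does not say that truncated subjects will be dropped. That is correct, and it is why the working shows both directions. Exclusion lifts the 85% count only if the excluded subjects lack Week 25 data on the measure that then passes. Telemedicine visits drop the 6MWT but keep actigraphy (Protocol 3.3.1.4 and 7.4), so site closures alone need not cause that loss.

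Finally, the sponsor is blinded to arm. That answers a charge of choosing by treatment result. It does not hide who has missing data, which is what the two rules count; SAP 9.3.1.1 says that daily actigraphy summaries were available to the sponsor during the study.

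**Conclusion.** The concern holds in a limited form. For one cohort, the visible plan leaves membership of three sets of analysis populations to individual sponsor decisions. It shows no criterion, and no deadline before the first adaptive count or the interim. This fits poorly with the visible rules on the FAS and on use of all available data.

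A reader might infer that the Type I error rate is inflated or that the sponsor selected favourable subjects. The documents show neither. The risk is selection on completeness, in either direction. It affects the design or endpoint decision only when presence is close enough to 85% or 65% for the number excluded to matter. How close is unknown, because the cohort size is not given; N, k and v above are all assumptions. The possible shift of the estimate, about 2 to 3 m for ten exclusions against a planned 30 m, depends on the zero-effect assumption. The point is worth correcting, but it does not undermine the trial as a whole.

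**What to change.** Replace the case-by-case wording in three steps.

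1. Keep every randomized, dosed subject of this cohort in the primary FAS, use all available visits, and treat visits missed because of COVID-19 as missing.
2. Fix the denominator of each data-presence count before that count is made, for example all randomized subjects whose visit was due by the cut-off date.
3. Move exclusion of the cohort, as a whole, to a sensitivity analysis beside the per-protocol analysis in SAP 9.1.4.1.

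If objective criteria already exist in text that is not visible, cite them in the footnote, date them before the Adaptation 1 count, and reconcile them with the FAS.

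The cost is SAP wording and one extra sensitivity analysis. The real downside is that presence percentages may fall, which makes a switch of design or endpoint more likely.

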#### 10.3.5 Exploratory Analyses

#### 10.4 INTERIM ANALYSIS

An interim analysis is planned in a blinded fashion, at approximately 75% of subjects randomized, to assess the extent of missing primary efficacy endpoint data at the end of Treatment Period 2. The outcome of this analysis will inform a decision for the study to continue with the **Original Crossover Design** or switch to the **Contingent Parallel Design**. Full details of the adaptation procedures are specified in Section 10.2.1.

A single interim efficacy analysis will be conducted when at least 75% of the subjects (ie, ~100 subjects) have completed the 26-week Treatment Period, data are available for both Treatment Period 1 and Period 2 6MWD evaluations, and if the expected time to randomize the final (136th) subject is greater than 3 months. The expected time to randomize will be based on the average recruitment rate for the prior 6 months. This plan will allow early stopping for convincing evidence of benefit if recruitment is slow. A non-binding futility analysis will be conducted at the same time. The results of these analyses will be provided to the independent Data Safety Monitoring Committee (DSMC) by the independent external consultant for their review and recommendation. The DSMC Charter and SAP will contain the approach for projecting recruitment, as well as formal criteria for the interim analyses for efficacy and futility. The Sponsor will remain fully blinded throughout this process.

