5 SAMPLE SIZE CONSIDERATIONS

5.1 PLANNED STUDY

The **Original Crossover Design** is a 2x2 crossover study designed to have 90% power to detect a placebo-corrected mean change from baseline difference of 30 meters, assuming that the

standard deviation of differences is 85 meters² and using a 2-group t-test with a 0.01 2-sided significance level, with a sample size of 124 subjects (62 in each sequence group). To account for a discontinuation rate of approximately 10%, the total sample size will be approximately 136 subjects.

The **Contingent Parallel Design** is a parallel-group study designed to use an allocation ratio of 1:1 between inhaled treprostinil and placebo, with a sample size of 266 subjects (133 per treatment) that would provide at least 90% power at a significance level of 0.05 (2-sided hypothesis) to detect a 30 meter between-treatment difference in the change from baseline in 6MWD, assuming a standard deviation of 75 meters. To account for a discontinuation rate of approximately 15%, the total sample size will be approximately 314 subjects. Should there be a switch to the Contingent Parallel Design, the analysis plan described in Appendix 12.4 will be followed.

5.2 [REDACTED]

[REDACTED]

² Note. Due to the smaller sample size expected for the crossover design a more conservative standard deviation of the difference (85 meters) was assumed (compared to 75 meters for a parallel design).

assignment. All safety analyses will be performed on this Safety Population, unless otherwise specified.

A summary table presenting the number and percentages of subjects for each analysis population will be presented by treatment group. Subjects who are excluded from any analysis population will be listed with reason for exclusion. The Sponsor must approve this list before treatment is unblinded and thus before performing final analyses.

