9.1.1 Hypothesis Test

The analysis of the primary efficacy endpoint of peak 6MWD assesses if inhaled treprostinil will increase the distance traversed in the peak 6MWT at Week 12 relative to baseline compared to placebo in subjects with PH-COPD. The null and alternative hypotheses are:

$$H_0: \mu_1 = \mu_2$$

$$H_a: \mu_1 > \mu_2,$$

where μ_1 and μ_2 are the baseline-adjusted change from baseline in 6MWD of the inhaled treprostinil and placebo treatments, respectively.

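### The crossover design's interim futility boundary runs the wrong way: it is met when p is at or below 0.227, so a positive result counts as futile and a weak one does not

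*SAP*

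**What the plan says.** Protocol 10.4 leaves the rule to other documents: "The DSMC Charter and SAP will contain the approach for projecting recruitment, as well as formal criteria for the interim analyses for efficacy and futility". SAP 4.2 adds that "A non-binding futility analysis will also be conducted as part of the interim analysis", with results going from an independent statistician to the DSMC while the sponsor stays blinded.

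The SAP's only futility criterion is in 4.2.2: "The corresponding non-binding futility boundary is provided as p-value less than or equal to 0.227 for the interim analysis". The method named is Lan-DeMets with an O'Brien-Fleming shape. The sentence does not say whether the p-value is one- or two-sided, which direction of effect it refers to, or how much Type II error is spent.

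The efficacy rule stands in the same paragraph. At the interim, "the interim analysis will apply a 2-sided alpha level of 0.010 (75% information fraction"; at the end, "at the final analysis at a 2-sided alpha of 0.022", "with the overall Type I error rate at 2-sided alpha of 0.05". Section 9.1.1 defines benefit: the test asks whether "inhaled treprostinil will increase the distance traversed in the peak 6MWT at Week 12 relative to baseline compared to placebo". Appendix 12.4.2 gives the Contingent Parallel Design no futility boundary, so the SAP has no second statement to compare with this one.

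**The concern.** Efficacy and futility boundaries should divide the interim outcomes into three ordered zones: strong evidence of benefit, continue, and too little evidence to go on. Here both rules are met by small p. The efficacy zone (p at or below 0.010) lies wholly inside the futility zone (p at or below 0.227), and the results that should prompt a futility discussion lie outside it.

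The missing side is a second gap. A two-sided p carries no direction, so a clear result in favour of placebo gives the same p as a clear benefit. Reversing the inequality alone would not cure this, because 0.227 maps to two different Z values.

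At stake is the signal given to an unblinded committee that advises a blinded sponsor. If the intended reading has to be settled after the interim data have been seen, that choice is no longer pre-specified.

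**Working it through.** **Inputs.** Effect 30 m, SD of differences 85 m, 124 evaluable subjects, 90% power at two-sided 0.01 (SAP 5.1). Interim at 75% information, efficacy p of 0.010 or less, futility p of 0.227 or less (SAP 4.2.2). Evaluable number at the look taken as 0.75 × 124 = 93, which is an assumption; SAP 4.2 says about 100, so that is shown too.

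**1. Sample size, as a check on the model.** The plan says the study is "designed to have 90% power to detect a placebo-corrected mean change from baseline difference of 30 meters". Normal approximation: n = (85/30)² × (2.576 + 1.282)² = 119.4. With the noncentral t distribution, 124 subjects give 90.3% power. The plan's figure reproduces.

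**2. The value 0.227.** For Lan-DeMets O'Brien-Fleming spending, the Type II error spent at information fraction t is 2[1 − Φ(z₁₋β/₂/√t)]. With β = 0.10 and t = 0.75 this is 2[1 − Φ(1.645/0.866)] = 0.0575. The futility boundary is Z = Φ⁻¹(0.0575) + θ√t, where θ is the drift at full information. With the fixed-sample drift θ = 1.960 + 1.282 = 3.24, Z = −1.576 + 2.807 = 1.23. Variants:

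| Setting (one-sided alpha) | Boundary Z | Two-sided p |
|---|---|---|
| 0.025, 90% power, non-binding | 1.33 | 0.182 |
| 0.025, 90% power, fixed-sample drift | 1.23 | 0.218 |
| 0.025, 95% power, non-binding | 1.22 | 0.222 |
| 0.025, 95% power, binding | 1.19 | 0.232 |
| 0.05, 80% power, non-binding | 1.20 | 0.2285 |
| 0.025, drift from 124 subjects, non-binding | 1.15 | 0.252 |

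None gives exactly 0.227. Because the SAP states neither β nor the side, the value can be neither confirmed nor called wrong. In every variant the futility zone is Z **below** the boundary, which means p **above** the cut-off.

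**3. The rule as written, at the planned effect.** Mean of the interim Z = 30 × √93/85 = 3.40. A two-sided p of 0.227 is |Z| = 1.208; a one-sided p of 0.227 is Z = 0.749.

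- Futility met, two-sided p: Φ(3.40 − 1.208) = 98.6%.
- Futility met, one-sided p: Φ(3.40 − 0.749) = 99.6%.
- Efficacy met, and therefore both met: Φ(3.40 − 2.576) = 79.6%.
- With 100 subjects the mean Z is 3.53; futility (two-sided p) is met in 99.0% and both rules in 83.0%.

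**4. The rule as written, with no effect.** P(p ≤ 0.227) = 22.7%, so 77.3% of trials with an ineffective drug do not trigger futility.

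**5. What the side changes.** The standard error at the look is 85/√93 = 8.81 m. The cut-off is 1.208 × 8.81 = 10.6 m if two-sided, and 0.749 × 8.81 = 6.6 m if one-sided.

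**6. The inequality reversed (futile if p > 0.227).** At the planned effect futility is signalled in about 1.4% of trials (two-sided p) or 0.4% (one-sided p). With no effect it is signalled in 77.3% on either side. On a two-sided p, however, half of the remaining 22.7%, or 11.35%, are results favouring placebo that escape the rule. A directional rule, Z below 1.208, would signal futility in 77.3% + 11.35% = 88.65% of trials with no effect.

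**The case against.** The strongest reply is that this is a slip of wording. The SAP says the boundary is given as this p-value; it does not say to stop when p is at or below it. The sentence would make sense if p ≤ 0.227 were the region in which to continue, or if p were one-sided towards harm. Two-sided values of 0.218 to 0.232 under several ordinary settings suggest a conventional boundary with the inequality written backwards. A competent statistician would query a rule that calls an efficacy crossing futile.

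The reach is also limited. The rule is non-binding. The look takes place only in the crossover design, and only if the last randomization is projected more than 3 months away and at least 90% of the 6MWD data are present. The DSMC charter, which is not available here, may state the rule correctly. The direction of benefit is defined in 9.1.1.

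Most of this stands, and it bears on how likely harm is. It does not make the text right. The SAP gives none of the rescuing readings, and 4.2 describes the charter's added detail as mainly process. Section 9.1.1 defines the hypothesis but does not attach a direction to 0.227. It is also fair that the rule is not wholly silent when the drug does nothing: 22.7% of such trials would meet it. The accurate statement is that an interim p above 0.227 does not.

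**Conclusion.** The concern holds. As written, the futility criterion is met by strong evidence and missed by weak evidence, and it contains the whole efficacy region. Read literally on a two-sided p, it is met in 98.6% of trials at the planned effect, and 79.6% meet both rules; with no effect, 77.3% do not trigger it. These figures assume a normally distributed interim Z, SD 85 m and 93 evaluable subjects; 100 subjects changes them little. The finding on direction depends on none of these assumptions, nor on the exact value 0.227. Type I error is not affected. The percentages measure the rule applied literally; they do not predict what the DSMC would do. Because this is a pre-specified decision threshold and correcting it costs little, it must be fixed before any interim look.

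**What to change.** Replace the sentence in SAP 4.2.2 with a directional rule: futility may be considered if the interim Z favouring treprostinil is below b, equivalently if the one-sided p exceeds the stated value. Give b, its side, the matching difference in metres, and the Type II error that is spent. Keep the rule non-binding and copy the same text into the DSMC charter.

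Re-run the boundary software once to obtain b. The efficacy levels should be settled in the same run. For a one-sided 0.025, Lan-DeMets O'Brien-Fleming at 75% gives 0.0097 and 0.0221 one-sided, or 0.0193 and 0.0442 two-sided. The stated 0.010 and 0.022 therefore match one-sided levels although labelled two-sided; Appendix 12.4.2 gives 0.019 and 0.044 for the same fraction. That is a separate point, but it shows that the side of 0.227 cannot be inferred from its neighbours.

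The cost is one sentence in each of two documents and one software run.
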